11.3 Selection of Investigators and Training

Board-certified gastroenterologists in accordance with US and hospital guidelines will be considered for participation as investigators in this study. Physicians in training (residents, fellows) and physician assistants may assist the Study Investigator in any aspect of the procedure as per standard practices at his/her institution but will not participate in performing the colonoscopy.

Each Investigator participating in the clinical trial and the associated clinical study staff will receive training on the clinical protocol. This includes training on AE reporting, case report form (CRF) completion, and Good Clinical Practice (GCP), as well as the device and system (including procedural use, device characteristics, shelf life and storage requirements, warnings, and precautions), if applicable.

12.0 Study Procedures

12.1 Screening and Informed Consent

At the screening visit, subjects will be approached to review the study and obtain consent on the informed consent form (ICF) prior to any study procedures. The purpose of the study and the benefits and risks of the procedures will be explained to the subject and the consent process will be documented accordingly in the medical records. Subjects who agree to study participation must sign an IRB-approved ICF. Subjects will be informed that their participation in this study is voluntary and they may refuse to participate or discontinue from the study at any time. Subjects will be given the opportunity to ask the investigator questions so that they are informed about the research. A copy of the signed informed consent must be provided to the subject and the informed consent process will be documented in source documents.

If new information becomes available that may affect a subject’s decision to continue to take part in the study, this information will be discussed with the subject by the investigator.

On the day of elective outpatient colonoscopy, patients will be identified at the time of admission to endoscopy. At the time of admission patients will be asked about the color/clarity of their last bowel movement, which is standard of care. Patients presenting for colonoscopy and reporting brown stool will

Document Title: Randomized Controlled Study Comparing Colon Evaluation With The Pure-Vu System To A Standard Colonoscopy In Patients Who Are High Risk For Inadequate Bowel Preparation (“RESCue”)	Document No. CL00048	Version 1.0	Page 24 of 41
---	--------------------------------	-----------------------	---------------

be shown a laminated card with color photos of the clarity scale and will select the photo most representative of their most recent stool and this will be recorded. Those who select the brown fecal clarity Grade 1, 2, or 3 will then be offered entry into the study and, if interested, will be screened for eligibility. If eligible, informed consent will be obtained. Consented patients will be randomized to the Intervention or Control arm and the Colon preparation details will be recorded.

12.2 Randomization

Randomization to Intervention or Control arm will use stratification by site, endoscopist and blocking. Sites are expected to contribute approximately equal numbers of procedures, and no site will be allowed to contribute more than 50% of the target sample size. The randomization sequences will be provided in advance by the study’s statistician using an online system to obtain the randomization assignment and the corresponding colonoscope will be prepared. Randomization assignment will be recorded for each subject.

12.3 Screen Failures

A subject is considered enrolled in the study when the randomization has occurred. Only subjects who undergo the colonoscopy procedure, regardless of treatment arm, will be followed. Subjects who provide study consent, but then are determined to be ineligible will be considered screening failures and will not require additional study follow-up.

For screen failures, the following will be recorded: Age, gender identity, indication for colonoscopy, pre-procedure stool clarity grade, reason for screen failure.

12.4 Pre- Procedure

As standard operating procedure in the outpatient population setting, bowel preparation is prescribed for individuals undergoing a colonoscopy procedure. Although bowel preparations are prescribed, it is not a requirement that the subject completes the bowel preparation prior to the colonoscopy procedure for the study.

Prior to the procedure the patient will be asked to complete pre-colonoscopy questionnaire regarding willingness to pay for Pure-Vu recorded.

Document Title: Randomized Controlled Study Comparing Colon Evaluation With The Pure-Vu System To A Standard Colonoscopy In Patients Who Are High Risk For Inadequate Bowel Preparation (“RESCue”)	Document No. CL00048	Version 1.0	Page 25 of 41
---	--------------------------------	-----------------------	---------------

Demographics, medical and surgical history will be recorded: Colonoscope (adult/pediatric), age, BMI, gender identity, racial identity, indication for colonoscopy, preparation details (purgative, dose, administration schedule, and diet), pre-procedure stool clarity grade, medications, medical history, and abdominal and pelvic surgery.

12.5 Colonoscopy Procedure

The insertion during the colonoscopy procedure will be performed by the clinical study investigator(s), experienced in GI endoscopy according to local standard of care. In cases where upper endoscopy is planned, it will be conducted per the physician’s discretion. Monitored Anesthesia Care (MAC) sedation will be utilized and documented.

The Colonoscope will be prepared as per normal routine and the research assistant will cover the colonoscope before the patient enters the endoscopy room to keep him/her blinded to the study arm. This is uncovered once the patient is sedated. During the colonoscopy, standard flushing and suctioning (Control arm) or the Pure-Vu System (Intervention arm) will be used at the endoscopist’s discretion.

Pure-Vu data: After each Pure-Vu colonoscopy, information regarding the use of the Pure-Vu System (number of times the pump is used and the total duration of use in seconds) will be documented.

Specific situations occurring during colonoscopy

If the attempt to reach the cecum fails, the investigator shall have the option to perform the procedure with a pediatric or any other colonoscope he/she may choose without Pure-Vu. The subject will complete the study as planned. If a medical condition requiring treatment is detected during colonoscopy, the subject will be treated as per the standard care.

Post-Examination Follow-up

Subjects will be transferred to recovery room for observation per clinical site’s colonoscopy protocol and will continue his/her medical flow as per the standard of care. Follow-up will be conducted 1-3 business days after the procedure to verify that there has been no change in their clinical status and record their willingness to use the Pure-Vu System in the future. Before a subject is considered “lost to follow-up”, there must be at least two documented attempts to contact the subject.

Document Title: Randomized Controlled Study Comparing Colon Evaluation With The Pure-Vu System To A Standard Colonoscopy In Patients Who Are High Risk For Inadequate Bowel Preparation (“RESCue”)	Document No. CL00048	Version 1.0	Page 26 of 41
---	--------------------------------	-----------------------	---------------

13.0 Statistical Analysis

13.1 Sample Size Determination

Assuming 60% preparation adequacy in the Control arm, and 90% preparation adequacy in the Intervention arm, a total sample size of 80 participants (40 per arm) has 85% power (using 2-sided alpha 0.05). To account for an expected dropout rate of 10% per arm, 44 participants per arm will be enrolled, for a total of 88 patients.

13.2 Description of Statistical Methods

Basic demographic and other baseline characteristics will be collected and analyzed for all subjects. Summary statistics (mean, standard deviation, median, minimum and maximum for quantitative variables) will be presented for the total study population. Frequency tables for qualitative data will be provided.

All main analyses will follow the intent-to-treat principle.

Any deviation from specified statistical plan will be in addition to “per protocol” analysis and will be reported as such.

13.3 Primary Endpoint Analysis

The primary statistical hypothesis is that the cleansing level post cleansing with the Pure-Vu (Intervention arm) will be significantly improved as compared to the cleansing level post standard colonoscopy procedure (Control arm). The Intervention (Pure-Vu) and Control (standard colonoscopy) arms will be compared with respect to preparation adequacy (BBPS ≥ 2 in every segment). In case of incomplete procedure, the segments that are not evaluated due to dirtiness are assigned a score of 0. In case of non-evaluated segment due to anatomical challenges (stricture, mass, etc.) segments will be excluded from analysis.

The risk ratio was estimated along with a 95% confidence interval, and use the Mantel-Haenszel test with stratification by site to test whether preparation adequacy differs between the two arms (with a 2-sided alpha 0.05). All main analyses will follow the intent-to-treat principle. In case of substantial deviations from the protocol, secondary per-protocol analyses will also be carried out.

Document Title: Randomized Controlled Study Comparing Colon Evaluation With The Pure-Vu System To A Standard Colonoscopy In Patients Who Are High Risk For Inadequate Bowel Preparation (“RESCue”)	Document No. CL00048	Version 1.0	Page 27 of 41
---	--------------------------------	-----------------------	---------------

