Randomization	Randomization to Intervention or Control will use stratification by site, endoscopist, and blocking.

Document Title: Randomized Controlled Study Comparing Colon Evaluation With The Pure-Vu System To A Standard Colonoscopy In Patients Who Are High Risk For Inadequate Bowel Preparation (“RESCue”)	Document No. CL00048	Version 1.0	Page 8 of 41
--	--------------------------------	-----------------------	--------------

Eligibility Criteria	
Inclusion Criteria
 
1. Adults \geq age 222. Elective outpatient colonoscopy by participating gastroenterologist3. Stool clarity grade 1-3 at presentation for colonoscopy 
Exclusion Criteria
 
1. Not competent to consent2. Bleeding disorder – known or suspected3. Hereditary Gastrointestinal Cancer syndrome4. Known PT INR > 1.55. Known elevated PTT6. Anti-platelet agent or anticoagulant (other than aspirin or nonsteroidal agent) which has not been stopped for the colonoscopy7. Known platelet count $< 50,000$8. Known absolute neutrophil count $< 1,000$9. History of surgical colon resection10. Pre-colonoscopy intent to enter terminal ileum11. Prior incomplete colonoscopy due to technical & non- bowel preparation related reasons12. Regular use of non-topical steroid13. Pregnant14. Prisoner or institutionalized for any reason15. Psychiatric illness greater than mild16. Colonoscopy without anesthesia administered (MAC) sedation17. Diverticulitis18. Active inflammatory bowel disease (Crohn's, Ulcerative Colitis, or Indeterminate)19. Known or suspected colon stricture
Interim analyses	None

Document Title: Randomized Controlled Study Comparing Colon Evaluation With The Pure-Vu System To A Standard Colonoscopy In Patients Who Are High Risk For Inadequate Bowel Preparation (“RESCue”)	Document No. CL00048	Version 1.0	Page 9 of 41
---	--------------------------------	-----------------------	--------------

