9.2 Secondary Endpoints

1. Assess the willingness of consented subjects to pay for Pure-Vu prior to colonoscopy
 - a. Would want Pure-Vu bowel cleansing device to be used on day of colonoscopy if preparation were inadequate (“Yes” or “no”)
2. Colonoscopy procedural measures for Intervention and Control arms
 - a. Duration: Insertion and withdrawal time without intervention other than cleansing

Document Title: Randomized Controlled Study Comparing Colon Evaluation With The Pure-Vu System To A Standard Colonoscopy In Patients Who Are High Risk For Inadequate Bowel Preparation (“RESCue”)	Document No. CL00048	Version 1.0	Page 20 of 41
---	--------------------------------	-----------------------	---------------

- b. Colonoscopy completion: “Yes” or “no;” if “no” then record most proximal extent of exam and reason exam was incomplete (it is acceptable to switch to a different scope if needed due to anatomical reasons)
- c. Polyp detection - For each polyp: Location, size, morphology (pedunculated, sessile, flat), removal technique (cold biopsy, hot biopsy, cold snare, hot snare, EMR), histology
- d. Non-polyp colonoscopy findings: Finding, location
- e. Assessment of need for early repeat colonoscopy (defined as endoscopist recommendation for early repeat colonoscopy due to preparation): “Yes” or “no”

3. Endoscopist experience

- a. Intervention arm
 - i. Ease of use of Pure-Vu (visual analogue scale 0-10)
 - ii. Efficacy of Pure-Vu (visual analogue scale 0-10)
- b. Intervention and Control arms
 - i. Technical difficulty performing colonoscopy (visual analogue scale 0-10)

4. Safety assessment for all subjects on the day of colonoscopy by endoscopist

- a. Type, incidence, severity, Relation to procedure and clinical consequence(s) of adverse event.

5. Post-colonoscopy patient experience with scripted phone call 1-3 days after colonoscopy

[figure not shown]
- a. Patient satisfaction
 - i. Colonoscopy experience overall (analogue scale 0-10)

6. Assess the willingness of consented subjects to pay for Pure-Vu 1-3 days after colonoscopy

[figure not shown]
- a. Would want Pure-Vu bowel cleansing device to be used in the future for colonoscopy if preparation were inadequate (“Yes” or “no”)

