13.4 Secondary Endpoints Analysis

Secondary dichotomous outcomes (intubation, adverse events) will be analyzed similarly using the Mantel-Haenszel test, with site as stratification variable (with a 2-sided alpha 0.05). Secondary continuous outcomes (timing, number of polyps, patient and endoscopist satisfaction) will be analyzed using linear regression, with site as a covariate.

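### Endoscopist is a randomisation stratum but is missing from the 13.4 linear models, which can cost power for operator-dependent continuous outcomes, chiefly procedure time

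*Combined protocol and SAP*

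**What the plan says.** Section 12.2 states: "Randomization to Intervention or Control arm will use stratification by site, endoscopist and blocking". The synopsis (3.0) says the same.

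Section 13.3 will "use the Mantel-Haenszel test with stratification by site to test whether preparation adequacy differs between the two arms". It ties site to the test and does not say whether the risk ratio is also stratified. Section 13.4 has two parts:
- "Secondary dichotomous outcomes (intubation, adverse events) will be analyzed similarly using the Mantel-Haenszel test, with site as stratification variable".
- "Secondary continuous outcomes (timing, number of polyps, patient and endoscopist satisfaction) will be analyzed using linear regression, with site as a covariate".

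Endoscopist appears in no main or sensitivity analysis, and no reason is given for leaving it out.

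Two endpoints in 9.2 plainly depend on who performs the procedure: "Duration: Insertion and withdrawal time without intervention other than cleansing" and "Technical difficulty performing colonoscopy (visual analogue scale 0-10". The second is the only endoscopist rating taken in both arms. Section 13.4 names timing but not technical difficulty; it speaks of endoscopist satisfaction, so it is an inference that the difficulty score goes into the same linear model.

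**The concern.** Balancing the arms within endoscopist removes differences between endoscopists from the treatment contrast. If the model then omits endoscopist, those differences stay in the residual variance. The standard error is then larger than the design warrants and the test is conservative.

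The protocol gives grounds to expect such differences. Section 5.1 describes colonoscopy as operator dependent, and 12.5 leaves the use of flushing or Pure-Vu to the endoscopist.

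At stake is power for outcomes such as procedure time, which the sample size in 13.1 was not chosen to serve. An endoscopist-adjusted result requested after the data are seen would also be post hoc.

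**Working it through.** **1. The plan's own figure.** Section 13.1: "Assuming 60% preparation adequacy in the Control arm, and 90% preparation adequacy in the Intervention arm", 40 per arm, two-sided alpha 0.05, stated power 85%. Exact enumeration of the two binomials gives 85.2% with Fisher's exact test, so the figure is reproduced. The unstratified Mantel-Haenszel test gives 90.1% without and 83.9% with continuity correction.

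**2. Primary endpoint: does omitting endoscopist matter?** Assumptions: 4 sites of 20 analysed (the plan allows up to 4 sites, roughly equal); 2, 3 or 5 endoscopists per site with equal caseloads, or 3 (70/20/10%) or 5 (50/20/10/10/10%) with unequal caseloads; blocks of 4; endoscopist effects normal on the logit scale. There were 20,000 simulated trials per setting. The table gives power for the uncorrected Mantel-Haenszel test stratified by endoscopist, pooling within site those with fewer than 6 subjects, minus power with site strata.

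| Endoscopist SD (logit) | 95% range of control adequacy across endoscopists | Change in power (points) | Site-only type I error |
|---|---|---|---|
| 0 | none | -0.7 to -0.2 | 5.0-5.1% |
| 0.5 | 37-80% | -0.5 to +0.2 | 4.7-5.0% |
| 1.0 | 19-92% | +0.3 to +1.2 | 4.0-4.3% |
| 1.5 | 9-97% | +1.1 to +2.2 | 3.2-3.7% |

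Full stratification without pooling costs up to 3.0 points at SD 0. For the dichotomous secondary outcomes (assumed 88% vs 98% and 2% vs 12%), full stratification changes power by -2.7 to +1.0 points. Finer strata therefore offer little for binary outcomes and can lose power.

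**3. Continuous outcomes: a closed-form check.** Set the within-endoscopist SD to 1. The endoscopist variance is then ICC/(1 - ICC). With 80 subjects balanced within endoscopist, the standard error of the arm difference is 2/√80 = 0.2236. An assumed effect of 0.68 SD gives 0.68/0.2236 = 3.041.

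- Site-only residual df: 80 - 4 - 1 = 75, critical t = 1.992. With k equal endoscopists per site, the expected residual variance is V = 1 + [80(k - 1)/k] × [ICC/(1 - ICC)] / 75.
- Site-only power ≈ Φ(3.041 - 1.992√V).
- Power with fixed endoscopist effects ≈ Φ(3.041 - t), with 79 - 4k df.

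Example, k = 5 and ICC 0.3: V = 1 + 64 × 0.4286/75 = 1.366, so 1.992 × √1.366 = 2.328. Site-only power is Φ(0.713) = 76.2%. Adjusted power (59 df, t = 2.001) is Φ(1.040) = 85.1%.

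| k | V, ICC 0.1 | Site-only / adjusted / loss | V, ICC 0.3 | Site-only / adjusted / loss |
|---|---|---|---|---|
| 1 | 1 | 85.3 / 85.3 / 0 | 1 | 85.3 / 85.3 / 0 |
| 2 | 1.059 | 83.9 / 85.2 / 1.3 | 1.229 | 79.8 / 85.2 / 5.4 |
| 3 | 1.079 | 83.4 / 85.2 / 1.8 | 1.305 | 77.8 / 85.2 / 7.4 |
| 5 | 1.095 | 83.1 / 85.1 / 2.0 | 1.366 | 76.2 / 85.1 / 8.9 |

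**4. Simulation.** Over the five layouts in step 2, a random endoscopist effect gained 1.2 to 1.9 points over site-only at ICC 0.1, 2.6 to 4.1 at ICC 0.2 and 4.6 to 8.1 at ICC 0.3. Fixed effects with equal caseloads gained about 6 to 9 at ICC 0.3. A separate simulation with other effect sizes and block sizes of 2 and 4 gave -0.4 to +2.2 at ICC 0.1 and +3.4 to +9.4 at ICC 0.3. Across these runs, site-only type I error at ICC 0.3 was 2.5 to 3.9%.

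**5. Dependence on effect size (ICC 0.3).** For 0.9 SD (0.9/0.2236 = 4.025) the formula gives losses of 1.3 to 2.3 points, and simulation about 2 to 3. For 0.45 SD (0.45/0.2236 = 2.012) the formula gives 8.5 to 12.8, and simulation about 8 to 12.

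**6. Cost of adjusting when endoscopists do not differ (ICC 0).** Fixed effects lose up to 3.9 points in simulation, where caseloads are uneven or endoscopists many. The random effect loses essentially none; its type I error was 4.8 to 5.6% over all settings.

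**The case against.** The case for leaving the plan alone is strong for most outcomes. Site-only analysis is pre-specified and valid. Only the primary endpoint is powered, so no stated secondary power is lost. Section 13.2 already provides for reporting departures from the plan as such. With the continuity-corrected test, which lies closer to the planned 85%, full endoscopist strata took primary power from 83.4% to 77.7% in one unfavourable layout (five unequal caseloads, no endoscopist effect). All of this stands, and it supports site strata for the primary and dichotomous tests.

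The power losses for continuous outcomes rest on assumed inputs and vary with effect size. That also stands, so they are shown only as illustration. The random-effect comparison is not size-adjusted: at ICC 0, where no real gain is possible, that model still showed 85.0 to 85.4% against 84.8 to 85.1%. This is a few tenths of a point and does not explain the gains at ICC 0.3.

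The objection does not remove the linear models. There the adjustment uses the groups already randomised, raises no sparse-table problem, and costs almost nothing as a random effect.

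A reader might infer that the mismatch makes the primary test invalid, casts doubt on a positive result or undermines the 85% power. The documents do not support this. Omitting a balanced stratum makes the test conservative, and step 2 shows that primary power hardly changes.

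**Conclusion.** This is a minor efficiency point that holds for the continuous secondary outcomes in 13.4. It applies chiefly to timing, and to technical difficulty if that score is analysed by the same linear model.

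At 0.68 within-endoscopist SD, with 80 analysed, 4 sites and 2 to 5 endoscopists per site, the loss is about 1 to 2 points at ICC 0.1 and about 5 to 9 at ICC 0.3. At ICC 0.3 it is about 2 to 3 points for a 0.9 SD effect and about 8 to 12 for 0.45 SD. It is nil if each site has one endoscopist, which the documents do not exclude. Number of endoscopists, caseloads, block size, ICC and effect sizes are all assumptions, so no single figure should be read as this trial's loss.

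The primary and dichotomous Mantel-Haenszel tests need no change.

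**What to change.** - **13.4, continuous outcomes:** add endoscopist nested in site to the linear models as a random effect, keeping site as a covariate. Fixed effects would do with two or three endoscopists per site of similar caseload. State whether technical difficulty is analysed by this model.
- **Data:** carry endoscopist into the analysis data set. It must be known at randomisation (12.2), but the items listed for recording in 12.4 do not name it.
- **13.3 and 13.4, binary outcomes:** keep site strata. A primary test stratified by endoscopist within site is optional as a pre-specified sensitivity analysis. It needs a pooling rule for endoscopists with few subjects (for example fewer than 6), fixed before outcomes are seen by arm.

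The cost is SAP wording, with no extra subjects. The downside is a few points of power at most with fixed effects, if there are many endoscopists who do not differ, and essentially none with a random effect.

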13.4 Secondary Endpoints Analysis

Secondary dichotomous outcomes (intubation, adverse events) will be analyzed similarly using the Mantel-Haenszel test, with site as stratification variable (with a 2-sided alpha 0.05). Secondary continuous outcomes (timing, number of polyps, patient and endoscopist satisfaction) will be analyzed using linear regression, with site as a covariate.

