7.0 Risk/Benefit Analysis

7.1 Anticipated Risks Associated with the Study Device conjunction with a colonoscope

The Pure-Vu is used in conjunction with a colonoscope during a colonoscopy procedure. Hence, the complications associated with using the Pure-Vu are anticipated to be similar to those associated with the colonoscopy procedure. As with any colonoscopy procedure, when using the Pure-Vu there are some risks

Document Title: Randomized Controlled Study Comparing Colon Evaluation With The Pure-Vu System To A Standard Colonoscopy In Patients Who Are High Risk For Inadequate Bowel Preparation (“RESCue”)	Document No. CL00048	Version 1.0	Page 18 of 41
---	--------------------------------	-----------------------	---------------

of a missed lesion, bowel perforation, pain, or bleeding. Although the risks of the procedure with the Pure-Vu System are expected to be comparable to conventional colonoscopy (0.35%), the device is an add-on to a colonoscope.

The Pure-Vu system was tested in an animal study including 35 pigs and in preliminary clinical studies including 97 subjects. No major complication or serious adverse events occurred within the course of those studies.

In addition, clinical studies demonstrated an excellent cleansing effectiveness; the Pure-Vu System improved the cleansing level from 25% at baseline to 99% after the cleansing was operated and in 98% of the subjects the cecum were reached and the procedures completed successfully.

Considering the residual risks and the potential and the risk against benefit assessment, it can be concluded that the system may offer potential benefit to the subjects along with no significant risk increase.

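### For serious and other low-rate adverse events, the site-stratified Mantel-Haenszel test and risk ratio in section 13.4 often cannot be computed and have negligible power; exact intervals by arm should carry the safety report

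*Combined protocol and SAP*

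**What the plan says.** Section 13.4 puts adverse events under the same rule as intubation: "Secondary dichotomous outcomes (intubation, adverse events) will be analyzed similarly using the Mantel-Haenszel test", with site as the stratifying variable and a two-sided alpha of 0.05. The word 'similarly' points back to section 13.3, which reads: "The risk ratio was estimated along with a 95% confidence interval, and use the Mantel-Haenszel test with stratification by site". The natural reading is that adverse events get a site-stratified risk ratio with a 95% confidence interval, and the test.

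Other sections also bear on safety reporting. Endpoint 4a in section 9.2 lists the type, incidence, severity, relationship and consequences of adverse events. Section 13.2 promises frequency tables for qualitative data. Section 14.8 has every adverse event recorded, whatever its severity or cause.

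The plan gives no rule for zero or very few events, no exact method, no interval for an arm's event rate or for the risk difference, no safety margin, and no power for adverse events. It does not say whether the Mantel-Haenszel statistic is continuity-corrected.

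**The concern.** The test was chosen for cleansing adequacy, where the plan expects 60% against 90%. Serious harms of colonoscopy are far rarer. With no events, the Mantel-Haenszel statistic is zero divided by zero. With one or two events, most sites contribute nothing, and the risk ratio is zero or infinite whenever one arm has none.

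The device is an add-on to the colonoscope, and section 6.3 reports a procedure-related rectal perforation in the inpatient study. Such events matter most for safety, and for them the stated inference would often yield either no result or a p-value that says little. A trial of this size can report how high an event rate its data still allow, and the plan does not ask for that.

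**Working it through.** **The plan's own figure.** Section 13.1 gives 85% power for 60% against 90% at 40 per arm. Fisher's exact test, fully enumerated, gives 85.2%, and the continuity-corrected chi-square gives 83.9%, so the figure is reproduced. It concerns cleansing only; there is no stated figure for adverse events to reproduce.

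**Inputs.** 44 per arm, 88 in total (13.1); up to 4 sites (synopsis), taken as 4 sites of 11 per arm. The documents state no expected adverse-event rate for this trial, so four figures from them are used as a range:

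- 0.35%, the procedural risk of conventional colonoscopy (7.1);
- 1/94 = 1.06%, serious events in the inpatient study (6.3);
- 4/94 = 4.26%, the one serious and three mild events in that study, assuming one event per patient;
- one third, the upper figure for minor symptoms after colonoscopy (5.1), if such symptoms are recorded as adverse events.

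**Formulas**, with the same rate p in both arms:

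- No event, test undefined: (1 − p)^88. At 0.35%: 0.9965^88 = 0.735.
- Risk ratio zero, infinite or undefined (at least one arm without events; equal arms within site): 1 − [1 − (1 − p)^44]^2. At 0.35%: 0.9965^44 = 0.857, so 1 − 0.143^2 = 0.980.
- Power: 200,000 simulated trials of the uncorrected site-stratified test.

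| Rate | Expected events in 88 | Test undefined | Risk ratio zero, infinite or undefined | Power for a doubling |
|---|---|---|---|---|
| 0.35% | 0.31 | 73.5% | 98.0% | about 0% |
| 1/94 | 0.94 | 39.0% | 85.9% | 1.0% |
| 4/94 | 3.74 | 2.2% | 27.3% | 12.0% |
| 1/3 | 29.3 | in practice never | in practice never | 88% |

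Power is 30% for a tripling from 4/94, and 35% for 33% against 50%.

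**Sensitivity.** With 80 subjects the test is undefined in 75.5%, 42.5% and 3.1% of trials at the three lower rates. An unequal site split of 22, 8, 7 and 7 per arm gives nearly the same results. The 1/94 comes from inpatients; section 7.1 reports no serious event in 97 earlier subjects. Pooling gives 1/191 = 0.52%, and (1 − 1/191)^88 = 0.63.

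**How many events the test needs.** Unstratified, with k events all in one arm of 44, the statistic is (k/2)² ÷ [44 × 44 × k × (88 − k) ÷ (88² × 87)], against a critical value of 3.84.

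- 3 against 0: 2.25 ÷ 0.733 = 3.07, not significant.
- 4 against 0: 4 ÷ 0.966 = 4.14, significant.
- 4 against 0 with a continuity correction: 1.5² ÷ 0.966 = 2.33, not significant.
- Fisher's exact test gives p = 0.12 for 4 against 0 and reaches significance only at 6 against 0 (p = 0.026).

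So with a handful of events, the result turns on a choice the plan does not make.

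**What intervals would show.** The exact (Clopper-Pearson) upper 95% limit for 0/44 is 1 − 0.025^(1/44) = 8.0%. Newcombe 95% intervals for the risk difference are about ±8.0 points for 0 against 0, and ±11.1 points for 2 against 2.

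**The case against.** The strongest objection is that 0.35% is the wrong rate for the variable tested. Section 13.4 tests adverse events, which section 14.1 defines as any untoward occurrence, related or not. A reader might infer from the 73% that the planned safety test usually fails. The documents do not support that for all events pooled: at 4/94 the test is undefined in about 2% of trials, and at one third in practice never. Nor is it without power everywhere, since 33% against 67% has 88%. This objection stands, and limits the point to serious and other low-rate events.

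A reader might also infer that the trial could end with no safety result. It could not: incidence and frequency tables are planned in 9.2 and 13.2 and would be produced whether or not the test can be computed. Those tables carry no measure of precision, however, and the risk-ratio interval carried over from 13.3 often fails at low counts.

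A third inference is that a non-significant test would be taken as proof of equal safety. No section says so. The statements in 7.1 and 7.3 that risk is not significantly increased are risk/benefit judgements made before the trial.

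Finally, low power for rare harms follows from a sample sized for cleansing, and exact intervals do not cure it. That is true, but they remain computable at every rate and show how little has been excluded. The objection also supports keeping the stratified test for pooled events.

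**Conclusion.** The point holds for serious and other low-rate adverse events. There the prescribed test has a 39% to 73% chance of being undefined, at assumed rates of 1/94 and 0.35%, and about 1% power or less for a doubling. At 4/94 it can nearly always be computed, but it has 12% power for a doubling and more than a quarter of trials give an unusable risk ratio. These figures assume 44 per arm, four equal sites, an uncorrected statistic, one event per patient for the 4/94, and earlier rates that carry over to this trial. The continuity correction lowers power further, to 3.6% for a doubling from 4/94.

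The documents do not support extending the point to all adverse events pooled, or reading the plan as a claim of equal safety. This is a cheap improvement to a secondary analysis, of low severity. The primary conclusion is unaffected.

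**What to change.** In section 13.4:

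- Make the adverse-event analysis counts and percentages by arm, with exact (Clopper-Pearson) 95% intervals and a 95% interval for the risk difference, given separately for any adverse event, procedure-related events and serious events.
- Do no hypothesis test for serious events.
- Keep the site-stratified Mantel-Haenszel test, if wanted, as a supplementary analysis of all adverse events pooled. State whether it is continuity-corrected.
- State in advance that 0/44 excludes only rates above about 8%, and that a non-significant adverse-event test is not evidence of comparable safety.

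The cost is a few sentences, one standard table and the loss of a p-value for serious events. No additional data or subjects are needed.
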